3.3.2 Inclusion criteria

- 1. 18 75 years at screening
- 2. Body weight ≤ 100 kg (at screening and at Day 1 of treatment)
- 3. Diagnosis of UC \geq 3 months prior to screening.
- Moderately to severely active UC as confirmed by Mayo Score ≥6 (with rectal bleeding ≥ 1 and modified endoscopy score ≥2) and elevated C-Reactive protein (CRP) or faecal calprotectin at pre-baseline visit.
- 5. Receiving conventional, non-biologic therapy for UC.

This therapy could consist of one or more of the following:

- Oral 5-ASA compound, with stable dose for at least 4 weeks prior to screening
- 6-MP, Methotrexate (MTX) or AZA, with stable dose for at least 8 weeks prior to screening
- Oral corticosteroids (≤ 20mg/day per day of prednisone or equivalent), with stable dose for at least 4 weeks prior to screening
- 6. Negative colon cancer screening by full colonoscopy with serial biopsies (or according to local standard of care) performed and documented within the past 12 months prior to screening (otherwise to be done at pre-baseline visit)
- 7. Patients who are naïve or experienced to TNF antagonists (including infliximab, adalimumab, or golimumab) but have not failed that treatment due to primary non-

response or loss of response (previous anti-TNF treatment outcome and reason for discontinuation must be documented in source data).

8. Women of childbearing potential and men able to father a child must use highly effective methods of birth control per International Conference on Harmonisation (ICH) M3 (R2) that result in a low failure rate of less than 1% per year when used consistently and correctly. A list of contraception methods meeting these criteria is provided in the patient information.

Note: A woman is considered of childbearing potential, i.e. fertile, following menarche and until becoming postmenopausal unless permanently sterile. Permanent sterilisation methods include hysterectomy, bilateral salpingectomy and bilateral oophorectomy. Tubal ligation is NOT a method of permanent sterilisation. A postmenopausal state is defined as no menses for 12 months without an alternative medical cause.

9. Signed and dated written informed consent in accordance with GCP and local legislation prior to admission to the trial

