6.2 IMPORTANT PROTOCOL DEVIATIONS

Data discrepancies and deviations from the CTP will be identified for all patients in the database (i.e., enrolled patients). Consistency check listings (for identification of violations of time windows) and a list of protocol deviations will be provided to be discussed at the RPM/DBLM/MQRM. At this meeting, it will be decided whether a discrepant data value can be used in analyses or whether it must be queried in the clinical database. Each protocol deviation must be assessed to determine whether it is an important Protocol Deviation (iPD). For definition of iPDs, and for the process of identification of these, refer to the BI reference document "Identify and Manage Important Protocol Deviations (iPD)" (2).

If any iPDs are identified, they are to be summarised into categories and will be captured in the RPM/DBLM/MQRM minutes via an accompanying Excel spreadsheet. The following Table 6.2: 1 contains the categories which are considered to be iPDs in this trial. If the data show other iPDs, this table will be supplemented accordingly by the time of the RPM/DBLM/MQRM. Not all iPDs will lead to exclusion from analysis sets. iPDs leading to exclusion from analysis sets are indicated as such in Table 6.2:1.

iPDs will be summarised and listed for the entered set.

TSAP for BI Trial No: 1368-0004 Page 15 of 48 Proprietary confidential information © 2019 Boehringer Ingelheim International GmbH or one or more of its affiliated companies

Category / Code	Description	Comments	Excluded from ¹
Α	Entrance criteria violated		
A1	Inclusion criteria not met		
A1.01	Age out of range	Inclusion criterion 1 Also check versus derived age	None
	LABEL: Age beyond 18-65	for patient.	
A1.02	Body weight out of range	Inclusion criterion 2	None
	LABEL: Body weight larger 100 kg	Also check versus reported body weight for patient	
A1.03	Diagnosis of UC <3 months prior to screening	Inclusion criterion 3 Also check derived time since diagnosis for patient	None
	LABEL: Diagnosis only recent		
A1.04	Moderately to severely active UC not confirmed, e.g. Mayo Score ≤ 6 and/or no elevated C-Reactive protein (CRP) or faecal calprotectin at pre-baseline visit.	Inclusion criterion 4 Also check derived total MCS,CRP and faecal calprotectin at pre-baseline	CAS
	LABEL:	Manual check in addition.	
	Disease activity not moderate or severe		

Important protocol deviations Table 6.2: 1

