PV will be detected manually Source: BI reference document: "Identify and Manage Important Protocol Deviations (iPD)" [001-MCS-40-413] (2). ¹ See Section 6.3 for population definitions

TSAP for BI Trial No: 1368-0004 Page 16 of 48 Proprietary confidential information © 2019 Boehringer Ingelheim International GmbH or one or more of its affiliated companies

Category / Code	Description	Comments	Excluded from ¹
A1.05	Receiving conventional, non-biologic therapy for UC. Concurrent UC treatments need to be on stable doses:	Inclusion criterion 5	CAS #
	This therapy could consist of one or more of the following:		
	 Oral 5-ASA compound, with stable dose for at least 4 weeks prior to screening 6-MP, Methotrexate (MTX) or AZA, with stable dose for at least 8 weeks prior to screening Oral corticosteroids (≤ 20mg/day per day of prednisone or equivalent), with stable dose for at least 4 weeks prior to screening LABEL: 		
	Concurrent UC treatment not on stable dose		
A1.06	Negative colon cancer screening within the past 12 months prior to screening not available	Inclusion criterion 6	None
	LABEL:		
	Lack of negative colorectal cancer screening		
A1.07	Patients who are naïve or experienced to TNF antagonists (including infliximab, adalimumab, or golimumab) but have not failed that treatment due to primary non- response or loss of response	Inclusion criterion 7	CAS
	LABEL:		
	Patient with previous TNF experience (non- response or loss of response)		
A1.08	Women of childbearing potential did not agree to use effective method of birth control; male patients did not agree to use condoms	Inclusion criterion 8	None
	LABEL:		
	Contraception methods not used		

Important protocol deviations (continued) Table 6.2: 1

PV will be detected manually

Source: BI reference document: "Identify and Manage Important Protocol Deviations (iPD)" [001-MCS-40-413] (2) ¹ See Section 6.3 for population definitions

TSAP for BI Trial No: 1368-0004 Page 17 of 48 Proprietary confidential information © 2019 Boehringer Ingelheim International GmbH or one or more of its affiliated companies

Categor Code	у/	Description	Comments	Excluded from ¹	
Α	A1.09	Signed and dated written informed consent in accordance with GCP and local legislation prior to admission to the trial LABEL:	Inclusion criterion 9– check for tick box only. Further PVs on informed consent are defined in section B below	All	
		IC not in accordance with legislation			
A2		Exclusion criteria violated			

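### SAP deviation code A1.04 counts a Mayo score of exactly 6 as failing entry and flags it for exclusion from the CAS, although the protocol admits that score

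*SAP*

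**What the plan says.** Protocol section 3.3.2, criterion 4, requires "Moderately to severely active UC as confirmed by Mayo Score ≥6", together with minimum rectal bleeding and endoscopy subscores and a raised CRP or faecal calprotectin. A total of 6 therefore satisfies the Mayo-total part.

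SAP section 6.2, Table 6.2: 1, lists deviations from this criterion under code A1.04, in the block headed "Inclusion criteria not met". The description reads "Moderately to severely active UC not confirmed, e.g. Mayo Score ≤ 6 and/or no elevated C-Reactive protein (CRP) or faecal calprotectin at pre-baseline visit". The comments cell names inclusion criterion 4 and adds "Also check derived total MCS,CRP and faecal calprotectin at pre-baseline" and "Manual check in addition". The last column reads CAS.

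The same SAP section gives the table its force: "iPDs leading to exclusion from analysis sets are indicated as such in Table 6.2:1". SAP section 6.3 removes from the CAS any patient with a deviation so flagged and names the CAS as the main set for the primary endpoint. Section 7.4 evaluates the primary endpoint on it. SAP section 4, which lists changes to the planned analysis, mentions no change to the entry threshold.

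**The concern.** A deviation rule should be the negation of the criterion it polices. The negation of a total of at least 6 is a total below 6. A1.04 says at most 6, so a patient with exactly 6 meets the entry rule and also matches the description of failing it.

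If the printed operator is used, three things follow for that patient:

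- The important-deviation table counts an inclusion violation that did not happen.
- The patient leaves the CAS, and so leaves the main primary analysis.
- The patient is not replaced, because protocol section 7.7 provides replacement only for early withdrawal from treatment.

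Protocol section 7.3 describes the primary gene-expression set as completers with evaluable baseline and post-baseline RNA, and leaves the details to the SAP. A completer who entered with a score of 6 fits that description.

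**Working it through.** The plan states no figure to reproduce here, and the sample size is not based on power.

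**1. The two rules.** The Mayo total runs from 0 to 12 (protocol appendix 10.1). Whole-number totals that satisfy both ≥ 6 and ≤ 6: {6}. Totals that satisfy both ≥ 6 and < 6: none.

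**2. Is it house style or an extraction fault?** Neighbouring numeric rows use the strict complement. Criterion 2 is weight up to 100 kg, and A1.02 flags weight above 100 kg. Criterion 3 is at least 3 months since diagnosis, and A1.03 flags less than 3 months. A1.04 breaks this pattern.

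**3. Is the row operative?** Some rows restate the criterion and make sense only under the block heading, for example A1.05 ("Receiving conventional, non-biologic therapy for UC. Concurrent UC treatments need to be on stable doses") and A1.07 ("Patients who are naïve or experienced to TNF antagonists"). Those rows list no check on a derived value, and A1.09 relies on a tick box. A1.04 is different: it is worded as a failure and calls for a check on the derived total. That check needs a cut-off, and the only Mayo cut-off printed in the row is ≤ 6.

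**4. Can an eligible patient score 6?** Take whole-number subscores with stool frequency 0–3, bleeding 1–3, physician's assessment 0–3 and endoscopy 2–3.

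- Profiles: 4 × 3 × 4 × 2 = 96
- Total below 6: 14, leaving 96 − 14 = 82 that meet the Mayo conditions of criterion 4
- Total exactly 6: 15 of the 82 (for example 1 + 1 + 2 + 2)

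This counts profiles and is not a probability. The documents do not give the share of patients at 6. If that share p is assumed, the chance of at least one among 10 is 1 − (1 − p)^10: 40% for p = 5%, 65% for p = 10%, 89% for p = 20%.

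**5. Cost to the primary analysis.** Each patient contributes one baseline sample (protocol section 7.3.1) and five post-baseline samples (V2, V3, V4, V7 and EoT; SAP section 7.4). The model has subject and time as factors. With complete samples and equal counts and dispersion, the variance of a time-versus-baseline contrast is proportional to 2/n, so the standard error ratio is √(10/n). The number removed is assumed to range from 0 to 3.

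| Removed | n | Samples (6n) | Parameters (n + 5) | Residual df | SE ratio | Rise |
|---|---|---|---|---|---|---|
| 0 | 10 | 60 | 15 | 45 | 1.000 | 0% |
| 1 | 9 | 54 | 14 | 40 | 1.054 | 5.4% |
| 2 | 8 | 48 | 13 | 35 | 1.118 | 11.8% |
| 3 | 7 | 42 | 12 | 30 | 1.195 | 19.5% |

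All five contrasts per gene can still be estimated in every row. The Wald statistic is referred to a standard normal distribution (protocol section 7.3.1), so the residual degrees of freedom do not set the critical value. The standard error is the relevant column.

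**The case against.** The strongest reply is that the cut-off is an illustration, introduced by e.g., in a row that names criterion 4 and so imports the correct threshold. The cell also omits the bleeding and endoscopy conditions, so it cannot be a full programming specification. SAP section 6.2 starts from deviations from the protocol, and a patient who meets criterion 4 has not deviated. The row adds a manual check, and SAP section 6.3 leaves allocation to sets to the meeting before database lock. Wrongful exclusion would need all of these to fail. The FAS is untouched by the flag, Table 6.3: 1 lists the primary endpoint for it, and the trial is exploratory with no confirmatory test.

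Most of this stands as mitigation. It lowers the chance of harm, but nowhere does the SAP say that 6 is to be kept, and anyone checking against the table sees ≤ 6. The FAS run does not restore the CAS result or the deviation count, and section 7.4 places it among analyses that may be conducted.

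Two limits on the size also stand. The range of 0 to 3 patients is an assumption. Stool frequency and bleeding scores are averages of diary entries (protocol appendix 10.1), so unrounded totals need not be whole numbers and the profile count may not describe the derived score. The overlap is still at exactly 6.

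**Conclusion.** The concern holds. A1.04 carries a threshold that contradicts inclusion criterion 4 at one value, in a table that determines membership of the main primary-endpoint set. Excluding a patient who truly fails criterion 4 is legitimate; only the boundary is wrong.

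The consequence is conditional on the printed operator being applied to a patient with a total of exactly 6. Each such patient costs a tenth of the planned primary set. The first raises the standard error of every time-point contrast by 5.4%, given complete samples and equal counts and dispersion. The number of deregulated genes lost or gained cannot be derived from the documents. The safety set, the FAS results and the secondary endpoints are not affected. The wording mismatch is certain; the harm is possible but not established. It should be fixed.

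**What to change.** In SAP Table 6.2: 1, code A1.04, replace ≤ 6 with < 6, so that the printed cut-off is the complement of the Mayo-total part of criterion 4. The bleeding and endoscopy conditions are still covered only through the row's reference to that criterion. Any program already written for the derived-score check should be compared with the corrected operator.

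The cost is one character in one table cell, with no effect on patients or data collection.

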6.3 SUBJECT SETS ANALYSED

The following analysis sets will be defined for this trial:

- Enrolled set (ES) This patient set includes all patients who signed informed consent. It will be used for analyses of patient disposition.
- Entered set (ENTS)

This patient set includes all patients who signed informed consent and entered the trial. It will be used for analyses of patient disposition.

• Safety analysis set (SAF):

This patient set includes all patients in the ENTS who received at least one dose of study drug. It will be used for analysis of safety, demographic data, baseline characteristics and (certain) biomarkers.

• Completers analysis set (CAS):

This patient set includes all patients in the SAF who completed trial medication and trial through EOT visit (i.e. a visit date was reported within the time-window of Week 12 visit; cf. Table 6.7: 1) and who had a baseline and at least one post-baseline measurement available for any clinical efficacy endpoint (e.g. Mayo score or Robarts histopathology index) or any biomarker endpoint (e.g. gene expression and/or inflammatory biomarker) without any iPD flagged for exclusion from the CAS in the table above. If a patient has any rescue use on or after Visit 1b but prior to administration of first dose of BI 655130 then this patient will also be excluded from the CAS. This is the main analysis set for presentation of primary endpoint

• Full analysis set (FAS):

This patient set includes all patients in the SAF who had a baseline and at least one post-baseline measurement available for any clinical efficacy endpoint (e.g. Mayo score or Robarts histopathology index) or any biomarker endpoint (e.g. gene expression or inflammatory biomarker) without any iPD flagged for exclusion from the FAS in the table above (cf. Table 6.2: 1). If a patient has any rescue use on or after Visit 1b but prior to administration of first dose of BI 655130 then this patient will also be excluded from the FAS. This patient set will be used for (sensitivity) analyses of efficacy and biomarkers.

The discussion of all exceptional cases and problems and the decisions on the allocation of patients to populations will be made at latest at the RPM/DBLM/MQRM. These decisions will be documented in the RPM decision $\log (\underline{3})$.

Table 6.3: 1 illustrates the data sets which are to be used for each category class of endpoints, and the approaches used with regard to missing data. For explanation of the different methods of handling missing data, cf. Section 6.6.

Page 25 of 48

Proprietary confidential information © 2019 Boehringer Ingelheim International GmbH or one or more of its affiliated companies

Class of endpoint	ES	ENTS	SAF	CAS	FAS
Disposition	OR	OR			
Compliance			OR		
Exposure			OR		
iPDs		OR			
Demographic/ baseline characteristics			OR		
Primary endpoint				OC	OC
Secondary safety endpoint			OR		
Secondary (and further) clinical efficacy endpoints					OC
Secondary inflammatory endpoints					OC

Table 6.3: 1Patient sets analysed

	OR,
Further safety parameters	OC-IR

i) For explanation of the different approaches with regard to missing data see Section 6.6. OC = observed cases, OC-IR = observed cases including also values after rescue medication, OR = original results.

Note that the number of patients with available data for an endpoint may differ. For details, see section "Handling of missing data".

6.5 **POOLING OF CENTRES**

Given the low number of patients per centre and the primarily descriptive nature of the statistical analysis, separate analyses by centre are not meaningful and not desirable. All patients from all centres will be pooled for statistical analysis.

Listings, sorted by centre, will however be displayed.

6.6 HANDLING OF MISSING DATA AND OUTLIERS

The original results (OR) approach implies the presentation of data exactly as observed (not using time windows as described in Section 6.7 and not setting values to missing). OR analysis will be performed on parameters and endpoints that are not affected by patients' rescue medication use (e.g. plasma concentration level of BI 655130), or, if it is not meaningful to apply any imputation rule for the replacement of missing values.

Proprietary confidential information © 2019 Boehringer Ingelheim International GmbH or one or more of its affiliated companies

6.6.1 Withdrawals

For all patients, the reason for withdrawal from treatment (e.g., adverse event) must be recorded in the eCRF. These data will be included in the trial database and reported. The reasons for withdrawal from treatment will be reported as indicated on the eCRF.

6.6.2 Efficacy data

For the Mayo and RHI total scores, a missing item or component score will lead to a missing total score. However, individual items and subscores may be presented as applicable. It is not planned to impute missing data for any efficacy endpoint in this trial. Cf. Section 9.1 for details regarding the derivation of (clinical) efficacy endpoints.

Data censoring for rescue medication use

Rescue medication use will be identified on the eCRF. For the purpose of data censoring, the following scenarios are considered rescue therapy in this trial:

- Any medication taken (even single use) after first dose of BI 655130 and on or before end of the on-treatment period which is considered by the investigator to be rescue treatment (as per tick in the CRF);
- Any increase in the dose of background medication for UC after first dose of BI 655130 and on or before end of the on-treatment period (i.e. Treatment phase plus REP) which is considered by the investigator to be rescue treatment (as per tick in the CRF)

The following approach will be used to present the efficacy data:

• Observed cases (OC) approach will include all collected data (based on time windows as described in Section 6.7), with no imputation performed on the missing data. Such an OC approach will exclude all values measured after intake of a rescue medication (i.e. such values will be set to missing).

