4.2 OTHER TREATMENTS, EMERGENCY PROCEDURES, RESTRICTIONS

4.2.1 Other treatments and emergency procedures

Patients in this trial are required to be on conventional, non-biologic treatment for UC.

Conventional treatment may consist of one or more of the following drugs (cf. Section 3.3.2, inclusion criteria), which are therefore permitted concomitant medications:

- Oral 5-ASA compound, with stable dose for at least 4 weeks prior to screening and throughout the trial
- 6-MP, MTX or AZA, with stable dose for at least 8 weeks prior to screening and throughout the trial
- Oral corticosteroids (≤ 20mg/day per day of prednisone or equivalent), with stable dose for at least 4 weeks prior to screening and throughout the trial. For equivalent doses of corticosteroids, please cf. Appendix 10.3.

Dose has to be stable throughout the trial. In the event that a patient experiences an intolerable increase of UC, as deemed by the investigator, during the course of the trial, the decision whether or not to discontinue treatment (if applicable) and start rescue treatment should be taken in the discretion of the investigator and in discussion with the CML. Rescue treatment may be any new medication or any increase in dose of a baseline medication.

Stable doses of concomitant therapies for chronic conditions, for which neither the condition nor the treatment are judged to exclude the patient from participation (cf. Section 3.3.3) are permissible. All concomitant medications should be carefully evaluated by the investigator, and the CML should be contacted when there are questions regarding concomitant medications.

Details of all concomitant medication will be recorded in the eCRF, along with the main reason for prescription. In addition, all prior treatment for UC within 12 months of Visit 1a will be recorded.

Infusion reactions including anaphylactic reactions:

In case of infusion reactions including anaphylactic reactions emerging during or after infusion of BI 655130, the investigator should consider in accordance with severity of the reaction and local standard of care to

- Immediately interrupt the infusion
- Treat with systemic anti-histamines and i.v. steroids and in case of a severe allergic reaction (eg, anaphylactic reaction) epinephrine

Also draw a plasma sample for IgE and ADA as detailed in the Lab Manual (Section 10 of the ISF).

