For each AE, the investigator should provide the information requested on the appropriate eCRF pages and the BI SAE form, if applicable. The investigator should determine the causal relationship to the trial medication and any possible interactions between the trial medication and a Non-Investigational Medicinal Product / Auxiliary Medicinal Product

The following should also be recorded as an (S)AE in the CRF and BI SAE form (if applicable):

- Worsening of the underlying disease or of other pre-existing conditions
- Changes in vital signs, ECG, physical examination and laboratory test results, if they are judged clinically relevant by the investigator.

Boehringer Ingelheim		03 Apr 2019
BI Trial No.: 1368-0004		
c10710598-04	Trial Protocol	Page 49 of 82

If such abnormalities already pre-exist prior to trial inclusion they will be considered as baseline conditions and should be collected in the eCRF only. All (S)AEs, including those persisting after individual patient's end of trial must be followed up until they have resolved, have been assessed as "chronic" or "stable", or no further information can be obtained.

Pregnancy

In rare cases, pregnancy might occur in a clinical trial. Once a patient has been enrolled in the clinical trial and has taken trial medication, the investigator must report any drug exposure during pregnancy in a trial participant immediately (within 24 hours) by means of Part A of the Pregnancy Monitoring Form to the sponsor's unique entry point.

The outcome of the pregnancy associated with the drug exposure during pregnancy must be followed up and reported to the sponsor's unique entry point on the Pregnancy Monitoring Form for Clinical Trials (Part B).

The ISF will contain the Pregnancy Monitoring Form for Studies (Part A and B).

As pregnancy itself is not to be reported as an AE, in the absence of an accompanying SAE and/or AESI, only the Pregnancy Monitoring Form for Clinical Trials and not the SAE form is to be completed. If there is an SAE and/or AESI associated with the pregnancy an SAE form must be completed in addition.

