Categ Code		Description	Comments	Excluded from ¹	
D2		Prohibited medication use			
	D2.01	Use of restricted medication as per CTP Table 4.2.2: 1 on or after Screening or during the on-treatment period when not provided as a rescue treatment to stabilize a worsening disease condition- prior to or up to Week 12	If restricted medication is initiated during trial	CAS	#
		LABEL: Restricted medication prior to week 12			
	D2.02	Use of restricted medication as per CTP Table 4.2.2: 1 when not provided as a rescue treatment to stabilize a worsening disease condition – after Week 12	If restricted medication is initiated during trial	None	#
		LABEL: Restricted medication after week 12			
D3		Change in background medication			
	D3.01	Concurrent UC treatments need to be on stable doses during treatment:	Medical review	CAS	#
		Any dose change in background medication on or after Screening or during the on- treatment period unless it is due to rescue use or adverse event– prior to or up to Week 12			
		LABEL: Concurrent UC treatment not stable prior to Week 12			
	D3.02	Any dose change in background medication period unless it is due to rescue use or adverse event – after Week 12		None	#
		LABEL:			
		Concurrent UC treatment not stable after Week 12	Medical review		

Important protocol deviations (continued) Table 6.2: 1

PV will be detected manually

Source: BI reference document: "Identify and Manage Important Protocol Deviations (iPD)" [001-MCS-40-413] (2) ¹ See Section 6.3 for population definitions

TSAP for BI Trial No: 1368-0004 Page 23 of 48 Proprietary confidential information © 2019 Boehringer Ingelheim International GmbH or one or more of its affiliated companies

	egory /		~	-	
Cod	e	Description	Comments	Excluded from ¹	
Ε		Missing data None	Missing visits, evaluations, and tests will be considered missing data, not protocol deviations		
F		Study specific analysis			
F1		Other trial specific violation			
	F1.01	Incomplete diagnosis of ulcerative colitis	Medical review	CAS	#
		LABEL: Incomplete diagnosis of UC			
F2		Certain violations of procedures used to measure primary or secondary efficacy/biomarker data			
	F2.01	To be defined at the RPM, if applicable	Manual iPDs which have a potentially relevant effect on primary or secondary data	Any exclusion will be defined at the RPM/ DBLM/ MQRM.	#
G		Other safety related violations			
	G1	Pregnancy test not done for woman of child bearing potential		None	
		LABEL: Pregnancy test not done			

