6.6.6 RNA sequencing data

The OC approach (cf. Section 6.6.2) will be used to present the RNA sequencing data.

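### Values after added UC treatment are censored only if the investigator ticks rescue, so unticked use stays in the FAS and, by a narrower route, can reach the EoT biopsy of the primary analysis

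*SAP*

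**What the plan says.** **Censoring rule.** SAP 6.6.2 lists two rescue scenarios: any medication taken after the first dose, and "Any increase in the dose of background medication for UC after first dose of BI 655130". Each counts only if "considered by the investigator to be rescue treatment (as per tick in the CRF". The consequence is then stated: "Such an OC approach will exclude all values measured after intake of a rescue medication". SAP 6.6.6 says that the same approach "will be used to present the RNA sequencing data", so it also governs the primary endpoint.

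**Important deviations.** In SAP Table 6.2:1, D2.01 covers restricted medication up to Week 12 "when not provided as a rescue treatment to stabilize a worsening disease condition". D3.01 covers background dose changes up to Week 12 "unless it is due to rescue use or adverse event". Both carry exclusion from the CAS only.

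**Analysis sets.** SAP 6.3 makes the CAS the main set for the primary endpoint. Table 6.3:1 assigns clinical and inflammatory secondary endpoints to the FAS under observed cases. SAP 7.5.2.1 instead bases CRP, calprotectin and lactoferrin on the SAF.

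**Protocol.** Section 4.2.1 describes rescue by its content: "Rescue treatment may be any new medication or any increase in dose of a baseline medication". Section 5.3.5.2 lists among the events to be recorded as an (S)AE: "Worsening of the underlying disease or of other pre-existing conditions". Section 3.3.4.1 says a patient is to be withdrawn from trial treatment when disease worsening calls for added UC therapy or a higher baseline dose. Section 4.2.1 leaves that decision to the investigator's discretion, in discussion with the sponsor's local monitor.

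**The concern.** The trial has one arm and is open-label, so change from baseline is the only measure of effect. Censoring after rescue is the SAP's own protection against crediting BI 655130 with the effect of other UC treatment. That protection turns on a label applied by an unblinded investigator, not on the medication recorded. Where the label is missing, the deviation table protects the CAS but not the FAS, and its adverse-event exemption opens a gap in the CAS as well. The Week 12 remission proportion, the inflammatory markers and part of the primary gene-expression data could then include values taken on additional UC therapy.

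**Working it through.** The plan states no figure on this point, and the sample size of 10 has no power basis (Protocol 7.7), so there is nothing to reproduce. The check is a trace of the rules, followed by an illustration of size.

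**Step 1: trace.** All cases occur after the first dose and up to Week 12.

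| Case | Censored (SAP 6.6.2)? | Important deviation? | CAS | FAS |
|---|---|---|---|---|
| Background increase, ticked | Yes | No, exempt as rescue | Kept if completer, later values missing | Kept, later values missing |
| Background increase, unticked, not attributed to an AE | No | D3.01 | Excluded | Kept, values used |
| Restricted medication for UC, unticked | No | D2.01 | Excluded | Kept, values used |
| Background increase for UC worsening recorded as an AE, unticked | No | No, on a literal reading of D3.01 | Kept if completer, values used | Kept, values used |

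The FAS column follows from SAP 6.3. The only deviations flagged for the FAS are no study drug taken (C1.01) and the consent failures flagged for all sets (A1.09, B1). Using the SAF for the markers would not help, because it has no exclusion for D2.01 or D3.01 either.

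**Step 2: how far the last row reaches into the primary analysis.** Doses are at Day 1, Week 4 and Week 8. Post-dose biopsies are at Day 1 (4 hours), Day 4, Week 2, Week 8 (before that day's dose) and EoT. The CAS requires completed trial medication.
- If Protocol 3.3.4.1 is applied to an increase before the Week 8 dose, the patient does not complete medication and leaves the CAS.
- After the Week 8 dose all three doses have been given, so an increase between Weeks 8 and 12 need not prevent completer status. The only biopsy still to come is EoT.
- Earlier biopsies are at risk only if the patient stays on treatment under the discretion in Protocol 4.2.1.

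**Step 3: size for remission.** SAP 7 keeps patients with missing values in the denominator. A Week 12 remission after added therapy therefore counts if unticked and does not count if ticked, with n unchanged. Assume 10 patients in the FAS and the Wilson interval of SAP 7.5.2.1, with z = 1.96 and z² = 3.8416:

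centre = (p + z²/2n)/(1 + z²/n); half-width = [z/(1 + z²/n)] × √(p(1−p)/n + z²/4n²)

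- 0/10: centre 0.19208/1.38416 = 0.1388; half-width 1.4160 × √0.009604 = 0.1388; interval 0 to 27.8%.
- 1/10: centre 0.29208/1.38416 = 0.2110; half-width 1.4160 × √(0.009 + 0.009604) = 0.1931; interval 1.8 to 40.4%.
- 2/10, by the same formula: 5.7 to 51.0%.

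Each such case moves the estimate by 1/10 = 10 percentage points.

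**Step 4: frequency.** The documents give none. At assumed per-patient rates of unticked use of 5%, 10% and 20%, the chance of at least one in 10 patients is 1 − 0.95¹⁰ = 40%, 1 − 0.90¹⁰ = 65% and 1 − 0.80¹⁰ = 89%. These are chances of unticked use, not of a remission that follows it.

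**The case against.** The strongest reply is that safeguards exist and that the literal reading of D3.01 is strained.

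- **The tick reflects the Protocol.** Section 4.2.1 itself rests rescue on the investigator's judgement, and the tick records that judgement. This stands, but the analysis then has no check on a missing or wrong tick.
- **Context of D3.01.** D2.01 treats medication to stabilise worsening disease as rescue, so the adverse-event limb of D3.01 may be meant for other events. That is a fair reading of intent. The text does not say it, and Protocol 5.3.5.2 points the other way.
- **D2.01 mentions no tick.** Equating unticked with not rescue is an inference. It rests on SAP 6.6.2, which says rescue use is identified on the eCRF.
- **Backstops.** D3.01 is subject to medical review. F2.01 allows manually detected deviations, with exclusions decided at the data review meeting, and SAP 6.2 lets that meeting decide on discrepant values. Individual listings and displays of background dose changes should make a case visible among 10 patients. These are real safeguards, but none states a criterion for unticked rescue.
- **FAS convention.** Keeping deviators in a full analysis set is normal in a descriptive trial. Here, though, the same set is meant to drop post-rescue values, and it does so by label.
- **Text not shown.** SAP 6.6.5 and 9.1 are not in the text available and might add detail.

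**Conclusion.** The point holds as a gap in the wording, worth closing before database lock. Observed-cases censoring depends only on the tick. Unticked restricted medication or a non-exempt background change is therefore kept uncensored in the FAS, and an unticked increase for UC worsening can, read literally, stay in the CAS. For remission the bias is upward, by 10 percentage points per case if 10 patients are in the FAS. The frequency is unknown. The trial is exploratory and tests no hypotheses on clinical results, so the harm is a biased estimate, not an inflated type I error.

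A reader might infer more than the documents support:
- That the adverse-event exemption alters the censoring rule. It sits in the deviation table and only removes the CAS backstop.
- That restricted-drug values enter the CAS primary analysis. With rescue identified by the tick, D2.01 excludes those patients from the CAS.
- That every later biopsy is affected. If Protocol 3.3.4.1 is followed, it is mainly the EoT biopsy.
- That the gene count is biased towards a drug effect. This is not shown: a discordant patient could also raise dispersion and lower the number of genes passing the FDR threshold.

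**What to change.** Before database lock, amend the SAP as follows.

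1. In 6.6.2 and 6.6.6, derive the observed-cases trigger from eCRF concomitant-medication data: after the first dose, any new UC-active or restricted medication given for UC, or any increase in background UC medication, whether or not ticked. Apply it to both CAS and FAS.
2. Do not censor after medication given for a non-UC reason. Protocol 4.2.1 foresees i.v. steroids for infusion reactions, and Table 4.2.2:1 restricts parenteral steroids. A trigger on any restricted steroid could delete everything after Day 1 for one patient, 1/10 of the trial. Flag such cases and assess them in a sensitivity analysis.
3. In D3.01, state that UC worsening does not qualify for the adverse-event exemption.
4. Keep the tick-based version as a sensitivity analysis.
5. Reconcile SAP 7.5.2.1 (SAF) with Table 6.3:1 (FAS) for CRP, calprotectin and lactoferrin. Protocol 3.3.4.1 and 4.2.1 must also be reconciled on withdrawal; which clinical rule should apply is not a matter for this review.

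The cost is SAP text and programming. Protocol 4.2.1 already has the main reason for each prescription recorded in the eCRF, so no new data are needed. The downside is a few more values set to missing in a 10-patient trial.
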